7. ANALYSIS POPULATIONS

The following analysis populations will be used to complete the analyses of data.

Cross-over subjects will be handled differently for each type of analysis population, as described subsequently. In general, subjects from the control group who have an ablation procedure after the primary endpoint is met will not be analyzed as cross-over.

Intent to treat (ITT) population: The ITT subject population will include all

subjects randomized, where subjects will be classified by the group to which they are randomized, regardless of the treatment received. For the ITT population, cross-over subjects will be included in the Control Group per randomization. Lost-to-follow-up and withdrawn/early termination subjects will also be included in the ITT population.

Per protocol (PP) population: The PP subject population will include randomized subjects who satisfy the following criteria, according to the treatment actually received:

- **Test Group:** subjects who
 - have undergone RF ablation,
 - are treated with the study catheter (THERMOCOOL[®] Catheter Family),
 - are in compliance (no major protocol deviations that has an impact on scientific value of the study) with the study protocol, and
 - have been treated for the study-related arrhythmia.
- **Control Group:** subjects who
 - have started an investigator-prescribed AAD and completed the dose-loading period (2 weeks),
 - have not undergone RF ablation,
 - are in compliance (no major protocol deviations that have an impact on scientific value of the study) with the study protocol, and
 - have been treated for the study-related arrhythmia.

All analyses conducted in the PP population will be as treated analyses. For descriptive tables and simple inferential models with fixed treatment effects subjects who have undergone RF ablation will be included in the Test Group regardless of the original treatment assigned (original randomization). Thus, cross-over subjects will be included in the Test Group for PP analyses. For more complicated inferential analyses, models will be applied where treatment itself is included as time-dependent covariate (see section 10.2 and 10.6.4). The approach described above applies for all tables which do not summarize data by visit (e.g. for time to event endpoints and other endpoints calculated overall per-patient). For summaries by visit and repeated measurement models, cross-over subjects will be completely excluded.

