8.3 Derived Variables

Duration of AF [months]

Time between the recorded date of first AF and the date of randomization.

Time to persistent AF/AT

According to protocol, persistent AF/AT is defined as AF/AT lasting longer than 7 consecutive days or requiring termination by cardioversion after 48 hours. The primary endpoint is reached at the date of the first cardioversion after randomization (except cardioversion solely as part of a (re-)ablation procedure) or detection of persistent AF/AT by transtelephonic monitoring (TTM, performed between month 3 and month 36). The sponsor will review and adjudicate all events (progressions to persistent AF/AT), which were reported by the Investigator. Adjudication will already be performed for the interim analyses. All events where the sponsor confirmed in their final assessment that the primary endpoint was reached will be taken into account for analysis. The date at which the primary endpoint was reached will be taken as adjudicated by the sponsor or as reported by the Investigator (if no sponsor adjudicated date is available).

The protocol is not specific about the start date for time to event calculation. Originally according to SAP version 1.0 (which was applied for the interim analyses) time to event had been defined as the difference between randomization date and the date at which the endpoint was reached. However, after further discussion, it was decided to update the start date for time to event calculation for final analysis and to use date of procedure as start date for the test group, and date of randomization as start date for the control group.

This approach seems to be more appropriate and more conservative, as visit windows are calculated from date of procedure for test group. Otherwise, if time to event was calculated from date of randomization, test group would have longer follow-up period and longer time to each follow-up visit as control group.

If the primary endpoint is not observed during follow-up time, subjects will be regarded as censored at the completion visit/ last visit or at the last time TTM was recorded, whichever is later.

Time to persistent AF (HRS 2017)

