10.1 Primary Efficacy Variable Analysis

The primary analysis will be a Kaplan-Meier (KM) analysis for all subjects in the ITT population and account for censored observations. The primary effectiveness analysis will be performed in the ITT population, where the subjects will be attributed to the treatment group as randomized, regardless of treatment cross-over or post-randomization medical care. A log-rank test will be used to compare the hazard functions between the two groups at any observed event time. If observed, the median time to persistent AF/AT as well as the 95% confidence intervals will be reported by treatment group based on Kaplan-Meier estimates. The rate of survival without persistent AF/AT and rate of persistent AF/AT at 3 years follow-up as well as the 95% confidence intervals for both groups will be presented using the product limit estimate from the Kaplan Meier curve. Kaplan-Meier curves will be plotted.

The effect size is defined as the negative log of the hazard ratio (hazard rate of the Test Group over hazard rate of the Control Group): $\delta = -\log_e(\lambda_t/\lambda_c)$.

This study is to test the following hypothesis using a one-sided test at alpha equal to 0.025:

H0: $\delta \leq 0$

H1: $\delta > 0$

Null hypothesis: the hazard rate in the Test Group is greater than or equal to the hazard rate in the Control Group at observed event times during the follow-up period

Alternative hypothesis: the hazard rate in the Test Group is less than the hazard rate in the Control Group at observed event times during the follow-up period

Subjects will be considered to have an effectiveness success if they do not progress to persistent AF/AT through the 3-year follow-up period.

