10.2 PP analysis

The Kaplan-Meier analysis as described in section 10.1 will be repeated in the PP population (based on the as-treated principle).

Moreover, an inferential analysis using a Cox proportional hazards model will be performed in the PP subject population. For the Cox proportional hazards model, treatment itself will be modelled as a time-dependent covariate, i.e:

- for control group (without cross-over): treatment at time t is “control” at any time t
- for ablation group (without cross-over): treatment at time t is “ablation” at any time t
- for cross-over group: treatment at time t is control at any time t before cross-over and ablation at any time t after cross-over

The Cox proportional hazards model will be used to compare the hazard rate between the two treatment groups at observed event times.

The hazard ratio and its 95% confidence interval will be reported. Missing primary effectiveness endpoint data will be censored at the time of the subject’s last visit/TTM.

The same principles outlined for section 10.1 also apply for section 10.2 (PP analysis).

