10.5 Sensitivity Analysis for the Primary Efficacy Variable

A sensitivity analysis will be performed using time to persistent AF (HRS 2017) as an alternative definition of the primary endpoint (see section 8.3). The analyses described in sections 10.1 to 10.3 will be repeated for this alternative definition. As this definition has not been investigated in any interim analysis, this sensitivity analysis will not need to be adjusted for interim looks. A one-sided alpha level of $\alpha=0.025$ will be used.

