14.2 EFFICACY DATA				
14.2.1.1	ITT	Time to Persistent AF/AT (Primary Efficacy Analysis) Results of Kaplan-Meier analysis and log rank test	16.2.17.1	2.1 (but without rates at 3 years and incl. conditional power)
14.2.1.2	ITT	Time to Persistent AF/AT (Primary Efficacy Variable)	16.2.17.1	2.2

Table Number	Population	Table Title / Summary	Supporting Listing	Interim Analysis Number
		Recalculated Operating Characteristics for Group Sequential Design		
	ITT	Time to Persistent AF/AT (Primary Efficacy Variable) Sample Size Re-Estimation	16.2.17.1	2.3 Only required for first interim analysis; not required for final analysis
14.2.1.3	ITT	Time to Persistent AF (HRS 2017) Results of Kaplan-Meier analysis and log rank test	16.2.17.1	
14.2.2.1	PP	Time to Persistent AF/AT Results of Kaplan-Meier analysis and log rank test	16.2.17.1	
14.2.2.2	PP	Time to Persistent AF/AT Cox regression analysis including treatment as time-dependent covariate	16.2.17.1	
14.2.2.3	PP	Time to Persistent AF (HRS 2017) Results of Kaplan-Meier analysis and log rank test	16.2.17.1	
14.2.2.4	PP	Time to Persistent AF (HRS 2017) Cox regression analysis including treatment as time-dependent covariate	16.2.17.1	
14.2.3.1	ITT	Time to Persistent AF/AT: Subgroup analyses Results of Kaplan-Meier	16.2.17.1	

Table Number	Population	Table Title / Summary	Supporting Listing	Interim Analysis Number
		analysis		
14.2.3.2	ITT	Time to Persistent AF (HRS 2017): Subgroup analyses Results of Kaplan-Meier analysis	16.2.17.1	
14.2.4.1	ITT, PP	Time to Persistent AF/AT by Number of Repeat ablations Results of Kaplan-Meier analysis	16.2.17.1	
14.2.4.2	ITT, PP	Time to Persistent AF/AT at 1 Year Results of Kaplan-Meier analysis and log rank test	16.2.17.1	
14.2.4.3	ITT, PP	Time to Persistent AF/AT at 2 Years Results of Kaplan-Meier analysis and log rank test	16.2.17.1	
14.2.4.4	ITT, PP	Time to Persistent AF (HRS 2017) by Number of Repeat ablations Results of Kaplan-Meier analysis	16.2.17.1	
14.2.4.5	ITT, PP	Time to Persistent AF (HRS 2017) at 1 Year Results of Kaplan-Meier analysis and log rank test	16.2.17.1	
14.2.4.6	ITT, PP	Time to Persistent AF (HRS 2017) at 2 Years Results of Kaplan-Meier analysis and log rank test	16.2.17.1	
14.2.5	ITT, PP	Number of Repeat Ablations	16.2.17.3	

Table Number	Population	Table Title / Summary	Supporting Listing	Interim Analysis Number
14.2.6	ITT, PP	Number of New AAD Drugs per Subject	16.2.17.3	
14.2.7	ITT, PP	Summary of Dose changes	16.2.22	

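### Fixed-group per-protocol (PP) tests count cross-overs as Test although they are event-free until ablation by definition; on the natural reading of SAP 7 this favours ablation

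*SAP*

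**What the plan says.** - **Grouping rule.** SAP 7 defines PP analyses as as-treated. For descriptive tables and simple models with a fixed treatment effect, "Thus, cross-over subjects will be included in the Test Group for PP analyses". On scope it adds: "The approach described above applies for all tables which do not summarize data by visit (e.g. for time to event endpoints" and other per-patient endpoints.
- **Who is a cross-over.** SAP 7 also says that, in general, "subjects from the control group who have an ablation procedure after the primary endpoint is met will not be analyzed as cross-over".
- **PP Control criteria.** The same section requires a PP Control subject not to have had RF ablation. It does not say what happens to a Control subject who progresses and is ablated afterwards.
- **Tests that use the grouping.** SAP 10.1 states "A log-rank test will be used to compare the hazard functions between the two groups at any observed event time", and SAP 10.2 repeats that analysis in PP on the as-treated principle. Table 14.2.2.1 (PP) is titled "Time to Persistent AF/AT Results of Kaplan-Meier analysis and log rank test". SAP 10.6.1 adds 1- and 2-year log-rank tests in both ITT and PP. For the HRS 2017 definition, SAP 10.5 says "The analyses described in sections 10.1 to 10.3 will be repeated for this alternative definition", and 10.6.1 repeats its own analyses too. SAP 10.6.4 fits PP Cox models with a fixed treatment effect.
- **Time origin.** SAP 8.3 decides "to use date of procedure as start date for the test group, and date of randomization as start date for the control group". It gives no start date for a cross-over moved to Test.
- **What already avoids the problem.** SAP 10.2 also plans a PP Cox model with treatment as a time-dependent covariate, and 10.6.4 ends with models of the same kind. The 1- and 2-year PP tests have no such counterpart.

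**The concern.** Group membership depends on what happens after randomization. A Control subject reaches the PP Test Group only by staying free of the endpoint until ablation. One who progresses first on drug is not a cross-over and, on the natural reading, remains in Control with the event. Control keeps the early events and gives up event-free time. The HRS 2017 repeats behave the same way, because AF sustained beyond 7 days already meets the protocol endpoint.

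The start date does not remove the problem. From randomization, event-free drug time is credited to Test. From the procedure, that time is dropped from Control.

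At stake is a set of PP p-values and hazard ratios printed beside the ITT result. A reader could take them as support for ablation when the grouping rule alone can produce them.

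**Working it through.** **Inputs from the documents.** 161 per arm, one-sided 0.025, 85% power, effect size 1.154, 50% cross-over, 10% drop-out over 3 years (SAP 6). 28 events and bound 2.0507 at the final look (SAP 10.4). Earlier trials had 42-59% cross-over in the first year (Protocol 8.3).

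**The plan's event count.** Events = 4(z_α + z_β)²/δ². With 4(1.960 + 1.036)²/1.154² the result is 27.0. With the final bound, 4(2.0507 + 1.036)²/1.154² gives 28.6, against 28 planned.

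**Assumptions.** No ablation effect; constant hazards; all subjects in PP; cross-over unrelated to risk; no delay to the Test procedure. The documents do not give cross-over timing. Two patterns are used: 50% spread over 3 years, or 50% all in year 1.

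**Closed-form check, 50% over 3 years.** A 3-year risk of 9.2% gives about 28 events.
- Event hazard λ = −ln(0.908)/3 = 0.03217. Drop-out μ = −ln(0.9)/3 = 0.03512. Cross-over c = ln 2/3 = 0.23105. Sum s = 0.29834.
- Each arm: events 161·λ/(λ+μ)·(1−e^(−3(λ+μ))) = 14.07, so 28.1 in total. Person-years 14.07/λ = 437.4.
- Control arm before any cross-over: events 161·(λ/s)·(1−e^(−3s)) = 10.27. Person-years 161·(1−e^(−3s))/s = 319.2.
- Of those, event-free drug time of later cross-overs: 161·c·[1−e^(−3s)(1+3s)]/s² = 94.3.
- After cross-over: 14.07 − 10.27 = 3.80 events in 437.4 − 319.2 = 118.2 person-years.

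| Grouping | Test rate | Control rate | Ratio |
|---|---|---|---|
| Fixed, clock from randomization | 17.87/649.9 = 0.0275 | 10.27/224.9 = 0.0457 | 0.60 |
| Fixed, clock from procedure | 17.87/555.6 = 0.0322 | 10.27/224.9 = 0.0457 | 0.70 |
| Time-dependent treatment | 17.87/555.6 = 0.0322 | 10.27/319.2 = 0.0322 | 1.00 |

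Simulated Cox hazard ratios for the two fixed groupings are 0.61 and 0.71, in agreement.

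**Simulated false positives, 3-year PP log-rank, one-sided 2.5%, 4,000 trials per scenario.** The three figures are for about 28, 46 and 77 events (3-year risk 9.2%, 15%, 25%).

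| Cross-over | From randomization | From procedure |
|---|---|---|
| 50% over 3 years | 28/39/55% | 17/23/32% |
| 50%, all in year 1 | 9/10/14% | 7/8/10% |
| 20% over 3 years | 8/9/13% | 5/6/8% |

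With 20% all in year 1 the figure is about 5%. On the same data ITT gives 2.1-3.1% and time-dependent treatment 2.4-3.2%.

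**1- and 2-year PP tests** (28 events over the full 3 years). With 50% cross-over in year 1: 15% at 1 year and 10% at 2 years (procedure date 10% and 7%). SAP 7 gives each subject one PP group. If later cross-overs therefore also count as Test, 50% over 3 years gives 28% and 32% (procedure date 17% and 18%).

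**Fixed-effect PP Cox treatment term (10.6.4).** With 50% over 3 years: HR 0.60-0.61 and 26/37/54% (procedure date 15/21/32%).

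**The other reading of SAP 7.** Suppose progressors who are later ablated leave PP, and ablation continues at the same rate after the endpoint (assumed). PP Control is then selected on ablation alone, so its rate returns to λ. The ratio is 0.0275/0.0322 = 0.85 from randomization and 0.0322/0.0322 = 1.00 from the procedure. At 28 events, simulated false positives are about 4% (year 1) to 7% (over 3 years), and about 3% with the procedure date.

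**The case against.** **The text does not settle the premise.** The bias needs progressors who are later ablated to stay in PP Control, yet SAP 7 bars ablated subjects from PP Control. Read literally, they leave PP, and most or all of the bias goes. A second literal reading puts anyone ever ablated in Test; Protocol 13.6 has no post-endpoint exception. That gives about 3% and a hazard ratio near 1.0. If ablation were three times likelier after progression (assumed), the direction would reverse: about 1.5 with exclusion, 1.8 if counted in Test. This objection stands. It makes the size conditional and shows that SAP 7 itself needs repair.

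**Confounding may pull the other way.** Protocol Appendix B ties cross-over to severe symptoms or side effects. With a shared log-normal risk factor and 50% cross-over (randomization date), the fixed-group null hazard ratio is 0.62-0.87 at SD 0.25, 0.70-0.99 at SD 0.5 and 0.96-1.62 at SD 1.0. This also stands: a reader might infer that the tests always favour ablation, and the documents do not support that. Nor is the time-dependent model free of confounding. Its null hazard ratio is 1.03-1.07, 1.13-1.21 and 1.50-1.97 in the same settings.

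**Much is already handled, and 50% may be too high.** The time-dependent models sit beside the 3-year tests, and the sponsor intends cross-over to be well below published rates. SAP 5.1 says the trial ended early, so 28 events and full follow-up are illustrative. These points reduce the weight. They do not make the fixed-group p-values interpretable, and the 1- and 2-year tests still lack an alternative.

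**Conclusion.** The point holds conditionally and should be fixed. On the natural reading of SAP 7, the grouping rule alone gives one-sided false-positive rates of about 9-28% (randomization date) or 7-17% (procedure date) at about 28 events and 50% cross-over, and about 5-8% at 20% cross-over (randomization date). These rest on assumed cross-over timing and on cross-over unrelated to risk. If later-ablated progressors leave PP, the 50% figures are about 4-7% and about 3%.

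A reader might infer that the trial's main result is compromised. It is not: the ITT primary analysis keeps cross-overs in Control, the stopping rules use ITT, and SAP 8.2 calls PP a sensitivity analysis. The time-dependent PP models (10.2, its HRS 2017 repeat, the end of 10.6.4) are free of immortal time.

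A reader might also extend the point to every term in the 10.6.4 models. No claim is made about baseline-covariate main effects. Interaction terms are affected only if cross-over differs strongly by the covariate: at 28 events and a two-sided 5% level, 40% v 60% cross-over gives 5%, while 30% v 70% gives 9%. No document figure supports such a split.

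**What to change.** 1. In SAP 7, state that Controls ablated after the endpoint stay in PP Control with their event, and reconcile this with the no-ablation criterion. Otherwise the time-dependent model also loses Control events.
2. Base PP treatment-effect inference on treatment as a time-dependent covariate. Add this model for the 1- and 2-year PP analyses and their HRS 2017 repeats.
3. Keep fixed-group PP Kaplan-Meier curves as descriptive only, without log-rank p-values. Add a note that cross-overs are event-free until ablation by definition, and state the start date used for them.
4. In 10.6.4, take the PP treatment effect from the time-dependent models at the end of that section. Do not interpret the treatment term of the fixed-effect PP models.
5. State that the time-dependent estimate can still be confounded by indication.

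Cost: SAP wording and a little programming. The start-stop dataset is already needed for 10.2 and 10.6.4, and no new data are required. The downside is a less simple PP figure and an estimate that can still be confounded. The propensity weighting of Protocol 13.11.1, which the SAP no longer includes, is a separate point.

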5. The recognized reasons for patients not doing well on drug therapy are as follows:
  - a. Patients failing to take the medication as prescribed – called “non-adherence”:
    - i. Missed days (drug holidays) – recurring disease symptoms or sudden drug-related side effects, if drug rebound effect, after resuming medication.
    - ii. Irregular timing, resulting in low concentrations of active drug at some points or too high concentrations of active drug when medication is taken at close intervals (may manifest as side effect problem).
    - iii. Medication dropout – patient takes no drug but does not share this information with his/her physician – unexpected disease progression.
  - b. Patient cannot tolerate medication, even if compliant with prescribed regimen (side effects):
    - i. Sensitivity to the prescribed AAD.
    - ii. Concurrent prescribed medications for other chronic diseases are contraindicated for the particular AAD prescribed.
6. When a subject complains to his/her Investigator about the medication and requests a cross-over to receive ablation, the Investigator will have little idea of the root cause of the subject's medication-related problem.

A cross-over management algorithmh could be used to help sort out disease progression issues from drug-related problems.

7. The following guidelines should be addressed by each investigator, prior to making a decision on a subject:

REASON TO INDUCE CROSS-OVER	REASON TO AVOID CROSS-OVER

 
1. Severe symptoms of AF in the absence of evidence that the subject was not taking the prescribed medication and consensus that further medication would be unsuccessful.
 
2. Severe side effects or AF symptoms, evidence of adherence to the prescribed AAD regimen, and no other drug options to which to switch the subject.
 
	
 
1. Evidence that the subject did not take the medications as prescribed and/or took concurrent incompatible medications for other chronic diseases – this subject should undergo Medication Managementi and then return to the hospital 3 weeks later for re-evaluation.
 
2. Evidence not sufficiently strong to merit cross-over, in the minds of the Investigator..
 

h A copy of this algorithm will be available to investigators in this trial as a reference guide to managing subjects with difficulties with their prescribed AAD.

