10.6.2 Number of Repeat Ablations and New AAD Drugs

To analyze this secondary effectiveness endpoint (number of repeat ablations and new AAD drugs per subject throughout 3 years follow-up), the number of repeat ablations will be summarized and listed for the subjects who have undergone at least one ablation. In addition, new AAD use (number of new AAD drugs per subject) and the frequency of dose changes will be summarized and listed for all subjects by treatment group. A new AAD will be defined as an AAD (class I or class III, or AV nodal blocking agents such as beta blockers (BB) and calcium channel blockers (CCB), which was started after randomization and which was not administered at baseline (i.e. there is no AAD entry with the same preferred term at baseline). The analyses will be performed on both ITT and PP populations. All medications will be coded by using the World Health Organization Drug Dictionary (September 2011 or newer) for this study. The number and percentage of subjects taking new AAD medications will be summarized by ATC level 2 and ATC level 4, overall and by treatment for the ITT and PP population.

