14.2.8	ITT, PP	New AAD Drugs – ATC classes	16.2.22	
14.2.9	ITT, PP	Heart Rhythm	16.2.17.3	
14.2.10.1	ITT, PP	Factors Associated With Time to Persistent AF/AT Results of Cox models with single baseline covariates	16.2.17.1	
14.2.10.2	ITT, PP	Factors Associated With Time to Persistent AF/AT Results of Cox model with multivariate baseline covariates	16.2.17.1	
14.2.10.3	PP	Factors Associated With Time to Persistent AF/AT Results of Cox models with single baseline covariates and treatment as time-dependent covariate	16.2.17.1	
14.2.10.4	PP	Factors Associated With Time to Persistent AF/AT Results of Cox model with multivariate baseline covariates and treatment as time-dependent covariate	16.2.17.1	
14.2.11.1	PP	Quality of Life – EQ5D Descriptive summary of VAS	16.2.14	
14.2.11.2	PP	Quality of Life – EQ5D	16.2.14	

Table Number	Population	Table Title / Summary	Supporting Listing	Interim Analysis Number
		Descriptive summary of changes from baseline in VAS		
14.2.11.3	PP	Quality of Life – EQ5D Results of repeated measurement model for changes from baseline in VAS	16.2.14	
14.2.11.4	PP	Quality of Life – EQ5D Frequency table for EQ-5D single items	16.2.14	
14.2.11.5	PP	Quality of Life – EQ5D Frequency table for changes from baseline in EQ-5D single items and results of Wilcoxon-Mann-Whitney test	16.2.14	
14.2.12.1	PP	Quality of Life – AFEQT Descriptive summary of derived scores	16.2.13	
14.2.12.2	PP	Quality of Life – AFEQT Descriptive summary of changes from baseline	16.2.13	
14.2.12.3	PP	Quality of Life – AFEQT Results of repeated measurement model	16.2.13	
14.2.13.1	ITT	Health Economic Analysis Number of hospitalizations	16.2.25	
14.2.13.2	ITT	Health Economic Analysis Length of hospitalizations	16.2.25	
14.2.13.3	ITT	Health Economic Analysis	16.2.25	

Table Number	Population	Table Title / Summary	Supporting Listing	Interim Analysis Number
		Number of unscheduled cardiovascular-related visits		

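### The PP tables of new AADs and dose changes report cross-over subjects' drug use before their ablation under ablation

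*SAP*

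**What the plan says.** **Group assignment.** Protocol 13.6 makes the PP analyses as-treated and counts anyone who had RF ablation in the Test Group. SAP 7 keeps this: "Thus, cross-over subjects will be included in the Test Group for PP analyses". It applies the rule to "all tables which do not summarize data by visit (e.g. for time to event endpoints and other endpoints calculated overall per-patient". PP Control keeps only subjects who were never ablated.

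**Exceptions.** SAP 7 adds: "For summaries by visit and repeated measurement models, cross-over subjects will be completely excluded". Control subjects ablated only after reaching the primary endpoint are not treated as cross-overs.

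**The count.** SAP 10.6.2 says that "new AAD use (number of new AAD drugs per subject) and the frequency of dose changes will be summarized" by treatment group. A new AAD is one "which was started after randomization and which was not administered at baseline". No other time window is given for dose changes. On populations: "The analyses will be performed on both ITT and PP populations". SAP 15.1 lists Tables 14.2.6 (number of new AADs), 14.2.7 (dose changes) and 14.2.8 ("New AAD Drugs – ATC classes") for both ITT and PP.

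**Drug use before cross-over.** Protocol 11.3 allows new AADs during the study. One of the two reasons for cross-over in protocol Appendix B, item 7, includes "no other drug options to which to switch the subject".

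**The concern.** Nothing in SAP 10.6.2 restarts the count at the ablation date or gives cross-over subjects their own column. A drug that a control subject started after randomization and before the cross-over ablation is a feature of drug therapy, yet the PP tables show it under ablation. PP Control loses the same subject, and with that subject the drug switching that preceded the cross-over.

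New AAD use is a listed secondary effectiveness endpoint with a planned PP analysis. A PP table could suggest more drug switching under ablation than under drug therapy, and disagree with the ITT table, through classification alone.

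**Working it through.** **1. Follow one subject.** A control subject starts a drug not taken at baseline at month 4 and crosses over at month 12. ITT: one new AAD under Control. PP: one new AAD under Test, none under Control.

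**2. Does another rule catch this?** The SAP handles cross-overs differently elsewhere:
- The PP Cox models with time-dependent treatment (10.2, 10.6.4) count time before cross-over as control.
- The subgroup Kaplan-Meier analysis (10.3) and the adverse drug reactions (11.5) show cross-overs as a third group.
- The PP rhythm summaries (10.6.3) exclude them.

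None of these provisions reaches Tables 14.2.6 to 14.2.8.

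**3. Inputs from the plan.** SAP 6 gives 161 subjects per arm and 50% cross-over. The 161 can be reproduced. The Rubinstein-Gail-Santner formula, with 3-year event-free proportions 0.85 and 0.95, 1.5 years of accrual and 4.5 years in total, gives 145.5 per arm. Dividing by 0.9 for drop-out gives 161.7. Only the equal arms and the 50% are used below. The documents give no expected new-AAD counts, so all drug means are assumptions.

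**4. Formulas.** Let p be the share of Control that crosses over. Let T and C be the mean new AADs per randomized Test subject and per never-crossed Control subject. Let b and a be the means per cross-over subject before and after ablation, and X = b + a. All subjects are assumed to meet the other PP criteria.
- ITT: Test = T; Control = (1 − p)C + pX
- PP as planned: Test = (T + pX)/(1 + p); Control = C
- Shift in the Test mean from adding cross-overs: p(X − T)/(1 + p), which is above zero whenever X > T
- Part of the PP Test mean that comes from drugs started before ablation: pb/(1 + p)
- PP comparison reverses when X > C + (C − T)/p

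**5. Results.**

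| T, C, b, a (assumed) | p | ITT Test v Control | PP Test v Control |
|---|---|---|---|
| 0.4, 0.5, 1.5, 0.2 | 50% | 0.40 v 1.10 | 0.83 v 0.50 |
| 0.2, 0.8, 1.5, 0.2 | 50% | 0.20 v 1.25 | 0.70 v 0.80 |
| 0.3, 0.5, 1.0, 0.2 | 50% | 0.30 v 0.85 | 0.60 v 0.50 |
| 0.4, 0.5, 1.5, 0.2 | 10% | 0.40 v 0.62 | 0.52 v 0.50 |
| 0.2, 0.8, 1.5, 0.2 | 10% | 0.20 v 0.89 | 0.34 v 0.80 |
| 0.3, 0.5, 1.0, 0.2 | 10% | 0.30 v 0.57 | 0.38 v 0.50 |

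First row: PP Test = (0.4 + 0.5 × 1.7)/1.5 = 0.83. Of this, 0.5 × 1.5/1.5 = 0.50 comes from drugs started before ablation.

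**6. When it reverses.** For T = 0.3 and C = 0.5, X must exceed 0.5 + 0.2/p: 0.90 at 50%, 1.17 at 30%, 1.50 at 20% and 2.50 at 10%. For T = 0.2 and C = 0.8, it must exceed 0.8 + 0.6/p: 2.0 at 50% and 6.8 at 10%. Across seven assumed sets of means, with T from 0.2 to 0.5, C from 0.5 to 0.8 and X from 0.7 to 1.8, the PP comparison reversed in six at 50% cross-over, three at 30%, two at 20% and none at 10%. The 10% reversal in the table (0.52 v 0.50) lies outside that set. It arises because T and C are assumed nearly equal.

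**The case against.** The strongest case on the other side is that little depends on these tables. Protocol 13.16 assigns this endpoint descriptive statistics, no test is planned, and the ITT version follows randomization. The as-treated rule is declared openly. The planned listings of ablation procedures, new AADs and cardiovascular medication would let a reader trace the mixing. All of this stands, and it limits the weight of the point. It does not correct the tables.

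It can also be said that cross-overs need not be heavy switchers during the study. The other reason in Appendix B, severe symptoms with agreement that further medication would not succeed, does not require exhausted drug options. Options may have run out before enrolment, since entry requires one or two failed drugs. Drugs started on or before the randomization date are baseline medication under SAP 9.4 and are not counted as new. This stands too: that cross-overs used the most drugs is plausible but not documented.

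A reader might infer that the PP table will reverse the true direction. The documents do not support that, because they contain no drug counts and reversal depends on them. Holding T and C close together makes reversal easy; the second row of the table, with the same cross-over counts, does not reverse. The 50% is a planning assumption, and Appendix B states the intent to keep cross-over well below published rates.

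**Conclusion.** The misattribution follows from the text: it occurs whenever a PP cross-over subject starts a new AAD or changes dose between randomization and the cross-over ablation. It affects three descriptive PP tables and runs against ablation whenever cross-overs start more new AADs per subject than randomized Test subjects. Its size is unknown. At 50% cross-over, reversal is possible under modest assumed counts but not certain. Near 10% it is unlikely, since it needs many drugs per cross-over subject or arm means that almost agree already.

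Two further inferences are tempting and should not be drawn. The drugs moved to Test need not have failed, because SAP 10.6.2 asks only for a start after randomization and absence at baseline. The rule is also not an invention of the SAP, because protocol 13.6 already contains it. The primary ITT analysis is not touched.

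**What to change.** In SAP 7 and 10.6.2, as a stated exception to protocol 13.6, show cross-over subjects as a separate third column in PP Tables 14.2.6, 14.2.7 and 14.2.8, as SAP 10.3 and 11.5 already do. Split their new AADs and dose changes into those before the cross-over ablation date and those on or after it. State that a drug first started before ablation and resumed afterwards counts once, at its first start, and that in Table 14.2.8 one subject may appear in both parts of the split.

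This leaves the PP Control definition unchanged, so no ablated subject has to be returned to that column. It does not make never-crossed controls comparable with Test; the ITT table remains the randomized comparison.

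The cost is SAP wording, a date comparison in programming, one extra column and smaller groups. Ablation procedures and cardiovascular medication are already in planned Listings 16.2.15 and 16.2.22.
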